3 STATISTICAL ANALYSES

3.1 GENERAL CONSIDERATIONS

Statistical significance for comparison between venglustat and placebo will be assessed at the Type I error rate of 0.05 one sided. Although a typical criterion for concluding that a trial is positive is a p-value of <0.05 two-sided, a higher Type I error rate of 0.05 one-sided was selected due to the rarity of late-onset GM2 gangliosidosis, the seriousness of this disease and lack of available therapy, as per Food and Drug Administration (FDA) draft guidance (1).

In general, continuous data will be summarized using the number of observations available, mean, standard deviation (SD), median, [Q1, Q3] minimum, and maximum. Categorical and ordinal data will be summarized using the count and percentage of participants.

The baseline value is defined as the last available value before or equal to the first dose of investigational medicinal product (IMP) date in the primary analysis period. For participants randomized but not exposed, the baseline value is defined as the last available value before or equal to the date of randomization.

Unless otherwise specified, analyses will be performed by intervention group (and overall for baseline and demographics characteristics).

The two analysis periods described below are defined:

- The **primary analysis period** is defined as the period starting at the date of signed informed consent, and ending at the end of Week 104 visit, or the day before the first IMP OLE administration (whichever comes last). For participants not exposed to IMP in the OLE, the primary analysis period ends at the date of end of study.
- The **OLE period** (only for participants exposed to IMP in the OLE) is defined as the period starting the day after the end of primary analysis period, until the end of the study.

Within each analysis period, the following observation periods are defined:

During the **primary analysis period** (as defined above), the following observation periods are defined:

- The **pre-treatment period** is defined as the time from the signed informed consent date up to the first IMP administration.
- The **treatment-emergent (TE) period** is defined as the time from the first IMP administration to the last administration of IMP during the primary analysis period +6 weeks (including any temporary treatment discontinuation period, if any) or the end of the primary analysis period (whichever comes first).

The TE period includes the following 2 periods:

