Simulations showed that the linear mixed-effect model is the most powerful approach when the distribution of individual slopes is normal but would be dramatically impacted in case a small proportion of participants exhibit an extreme slope. The Type I error rate of the linear mixed-effect model would also be inflated in presence of extreme slopes. The robust ANCOVA on individual slopes would be slightly less powerful if the distribution of individual slopes is normal, but very modestly impacted in presence of extreme slopes. The proposed approach with a pre-specified criterion for using the robust ANCOVA maintains the power close to 80% in all scenarios and protects against inflation of the Type I error rate. Details on the simulation is provided in [Section 5.6.3](#).

If the robust ANCOVA becomes the main analysis, the linear mixed-effect model will be produced as sensitivity analysis.

3.2.2.3 *Sensitivity analyses*

3.2.2.3.2 *Sensitivity to the logarithm transformation*

A sensitivity analysis will assess the impact of the logarithm transformation.

In this sensitivity analysis, the linear mixed-effect model will be fitted to the 9-HPT without logarithm transformation.

In case of presence of outlier, the linear mixed-effect model will be replaced by the robust ANCOVA on individual slopes, described in [Section 3.2.2.3.1](#). The exact criterion to detect outliers is presented in [Section 5.6.1.2](#).

Another sensitivity analysis will use the reciprocal of the 9-HPT.

3.2.2.3.3 *Sensitivity to the assumption of linear change*

A sensitivity analysis will assess the impact of the assumption of linearity of change. A mixed effect model with repeated measures (MMRM) with the categorical fixed factor of time (representing scheduled visits) will be used. Change from baseline in log-transformed 9-HPT at the different time-points will be included in this model, with the fixed effects of treatment group (venglustat versus placebo), time point (Week 12, Week 26, Week 52, Week 78 and Week 104) treatment-by-time point interaction as well as the continuous fixed covariate of log-transformed baseline 9-HPT.

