4 SAMPLE SIZE DETERMINATION

In the primary population, approximately 57 participants will be randomly assigned with a 2:1 randomization ratio to venglustat (n=38) or placebo (n=19). This sample size will provide approximately 80% power to detect a difference between venglustat and placebo with regards to the primary efficacy endpoint of annualized rate of change in 9-HPT.

Sample size and power calculations were based on simulations (see [Section 5.6.3](#) for details).

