5.6.2 Confidence interval for the difference in annualized rate of change in 9-HPT

The estimated difference in annualized rate of change in 9-HPT is defined as:

$$\hat{\delta} = \exp(\widehat{\beta_1}) - \exp(\widehat{\beta_0})$$

where $\widehat{\beta}_1$ and $\widehat{\beta}_0$ are the estimated slopes of log-transformed 9-HPT, for the venglustat and placebo arm respectively.

Using the properties of the log-normal distribution, it can be shown that $\exp(\hat{\beta}_l)$ have mean and variance m_i and v_i respectively, equal to:

$$m_i = \exp\left(\widehat{\beta}_l + \frac{Var(\widehat{\beta}_l)}{2}\right)$$

The 90% confidence interval of the difference in annualized rate of change in 9-HPT can be calculated as:

$$m_1 - m_0 \pm z_{0.95} \times \sqrt{v_1 + v_0}$$

where $z_{0.95}$ is the 95th quantile of the normal distribution.

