5.6.3.3 SAS code used to conduct the simulations

```

/*****************************;
/* STEP 1 : Definition of simulation parameters */;
/*****************************;

* Number of simulations;
%let Nsim = 10;

* Total number of patients on venglustat and placebo;
%let NpatV = 38;
%let NpatP = 19;

* List of time-points (in years) ;
%let listtime = 0,0.25,0.50,1,1.50,2.0;

* Seed of simulations ;
%let seed = 15299;

* Drop out rate (at time tdrop) ;
%let rdrop = 0.1;

```

```
%let tdrop = 2;

* Mean and SD of intercept ;
%let mI = 3.5551;
%let sdI = 0.4841;

* Mean slopes on Placebo ;
%let mS_P = 0.0273;

* SD of random slopes (between subject SD) ;
%let sdS = 0.0192;

* SD of residual error (within subject SD) ;
%let sdR = 0.0791;

* Scenarios for the difference in slope (list separated by commas);
%let diff = -0.0374,0;

* Number of scenarios for extreme values;
%let Nsce = 10;

* Base scenario (protocol assumption, no extreme patient ;
%let pE1 = 0;
%let mE1 = 0;
%let sE1 = 1;

* Scenario with 1% extreme patients having mean slope = 0.4;
%let pE2 = 0.01;
%let mE2 = 0.4;
%let sE2 = 0.0192;

* Scenario with 1% extreme patients having mean slope = 0.7;
%let pE3 = 0.01;
%let mE3 = 0.7;
%let sE3 = 0.0192;

* Scenario with 1% extreme patients having mean slope = 0.9;
%let pE4 = 0.01;
%let mE4 = 0.9;
%let sE4 = 0.0192;

* Scenario with 2% extreme patients having mean slope = 0.4;
%let pE5 = 0.02;
%let mE5 = 0.4;
%let sE5 = 0.0192;

* Scenario with 2% extreme patients having mean slope = 0.7;
%let pE6 = 0.02;
%let mE6 = 0.7;
%let sE6 = 0.0192;

* Scenario with 2% patients having mean slope = 0.9;
%let pE7 = 0.02;
%let mE7 = 0.9;
%let sE7 = 0.0192;
```

```
* Scenario with 5% extreme patients having mean slope = 0.4;
%let pE8 = 0.05;
%let mE8 = 0.4;
%let sE8 = 0.0192;

* Scenario with 5% extreme patients having mean slope = 0.7;
%let pE9 = 0.05;
%let mE9 = 0.7;
%let sE9 = 0.0192;

* Scenario with 5% extreme patients having mean slope = 0.9;
%let pE10 = 0.05;
%let mE10 = 0.9;
%let sE10 = 0.0192;
/*********************************************************************
/* STEP 2 : Simulation of clinical trial data under different scenarios */
/********************************************************************

/* Simulation of clinical trial data */
data SimData(keep=diff sce pE mE sE sim subject group base time log9hpt);
length diff sce pE mE sE sim subject group base time log9hpt 8;

retain seed &seed;

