  class group;
  id subject;
  model slope = group base;
  weight w;
  ods output ParameterEstimates=RobustParameterEstimates;
  output out=RobustPred predicted=pred stdp=SE sr=stdres;
run;

ods listing;
options notes;

/* Get estimate of difference of slopes and calculate 1-sided p-value */
data Robust;
  set RobustParameterEstimates;
  where parameter = "group" and Level1 = "1";
  RobustPvalue1S = probnorm(estimate/stderr);
  keep diff sce pE mE sE sim estimate stderr lowerCL upperCL RobustPvalue1S;
  rename estimate = RobustEst
        stderr    = RobustSE
        lowerCL   = RobustLower
        upperCL   = RobustUpper;
run;
```

```
run;

/* Calculate number of patients with weighted standardized residual greater
than 3 and greater than 4 */
data outlier;
  set RobustPred;
  where subject notin (99.1,99.2);
  outlier3 = (abs(W*stdres) > 3);
  outlier4 = (abs(W*stdres) > 4);
run;
proc means data=outlier nopolish nway;
  class diff sce pE mE sE sim;
  var outlier3 outlier4;
  output out=Noutlier(keep=diff sce pE mE sE sim nOutlier3 nOutlier4)
sum=nOutlier3 nOutlier4;
run;

/*************************************************/
/* STEP 5 : Combine results and report simulation results */
/*************************************************/

/* Combine results from the linear mixed model and from robust ANCOVA */
data AllResults;
  merge LMM Robust Noutlier;
  by diff sce pE mE sE sim;

  * Hybrid approach: use robust ANCOVA if at least one patient with
  standardized residual > 4 or at least 2 patients with standardized residual >
  3;
  * otherwise, use linear mixed-effect model ;
  if nOutlier4 >= 1 or nOutlier3 >= 2 then do;
    Robust      = 1;
    HybridEst   = RobustEst;
    HybridSE    = RobustSE;
    HybridLower = RobustLower;
    HybridUpper = RobustUpper;
    HybridPvalue1S = RobustPvalue1S;
  end;
  else do;
    Robust      = 0;
    HybridEst   = LMMEst;
    HybridSE    = LMMSE;
    HybridLower = LMMLower;
    HybridUpper = LMMUpper;
    HybridPvalue1S = LMMPvalue1S;
  end;

  * Determine if significant at 0.05 one-sided level ;
  LMMSign    = (LMMPvalue1S < 0.05);
  RobustSign  = (RobustPvalue1S < 0.05);
  HybridSign  = (HybridPvalue1S < 0.05);

  * Coverage of 95% confidence interval ;
  LMMCover   = (LMMLower < diff < LMMUpper);
  RobustCover = (RobustLower < diff < RobustUpper);
  HybridCover = (HybridLower < diff < HybridUpper);
```

```
* Bias in difference ;
LMMBias = LMMEst - diff;
RobustBias = RobustEst - diff;

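### The visible SAP code tests the robust ANCOVA against a normal rather than a t reference; this adds about 0.05 to 0.3 percentage points to the hybrid 9-HPT test's one-sided type I error

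*SAP*

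**What the plan says.** SAP Section 3.1 sets the significance level: comparisons "will be assessed at the Type I error rate of 0.05 one sided". Section 3.2.2.2 makes a mixed model on log 9-HPT the main analysis, with a robust ANCOVA on individual slopes taking over in the presence of outliers, and states that this approach "protects against inflation of the Type I error rate". The supporting simulations are in Section 5.6.3.

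The program in Section 5.6.3.3 forms the two p-values differently. Step 3 passes the mixed-model statistic to `probt` with the model's degrees of freedom. Step 4 uses "RobustPvalue1S = probnorm(estimate/stderr", with no degrees of freedom. Step 5 takes the robust p-value if at least one weighted standardized residual exceeds 4 or at least two exceed 3 in absolute value, takes the mixed-model p-value otherwise, and tests the result at 0.05.

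Section 5.6.2 builds the 90% interval for the difference in annualized rates from a multiplier that "is the 95th quantile of the normal distribution".

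The visible text of Section 3.2.2.2 names no degrees-of-freedom method for the mixed model. Section 3.2.2.3.3 names Kenward-Roger for the MMRM sensitivity analysis.

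**The concern.** The robust ANCOVA estimates an intercept, a treatment effect and a baseline slope from at most 57 individual slopes, and its scale is estimated from the same data. A normal reference treats that scale as known, so its critical value is a little too small. The error always goes the same way, toward rejection.

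The alpha level is already 0.05 one-sided, and the endpoint is co-primary. The robust branch matters most when some participants have extreme slopes, which is the situation the hybrid was built for. The same robust ANCOVA can become the main analysis for 25FWT and FARS-neuro (Sections 3.3.1.2.2 and 3.3.1.2.3). The simulated type I error that supports the Section 3.2.2.2 statement also comes from this p-value.

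**Working it through.** **Inputs (SAP Section 5.6.3.3).** 38 and 19 participants. Difference in log slopes under the alternative and the null: "let diff = -0.0374,0". Assessment times in years: "let listtime = 0,0.25,0.50,1,1.50,2.0". Random-slope SD 0.0192, residual SD 0.0791, intercept SD "let sdI = 0.4841". Exponential dropout reaching 10% at 2 years. Ten scenarios: no extreme slopes, or 1%, 2% or 5% of participants with mean slope 0.4, 0.7 or 0.9.

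**Step 1: the plan's own figure.** Section 4 says: "This sample size will provide approximately 80% power to detect a difference between venglustat and placebo" of approximately 80%.
- The mean assessment time is 0.875, so the centered sum of squares is 7.5625 - 6 × 0.875² = 2.96875.
- SD of an individual slope = √(0.0192² + 0.0791²/2.96875) = 0.04976.
- SE of the difference = 0.04976 × √(1/38 + 1/19) = 0.01398.
- Power = Φ(0.0374/0.01398 - 1.645) = 84.9% without dropout. With 10% fewer participants the ratio falls to 2.538 and power to Φ(2.538 - 1.645) = 81.4%.
- Full simulation, no extremes: mixed model 81.1%, hybrid 81.0 to 81.2%.

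The stated power is reproduced.

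**Step 2: ceiling on the effect of the reference.** With 57 slopes and 3 parameters there are 54 degrees of freedom. The one-sided 5% point is 1.674 for t and 1.645 for the normal. P(t54 > 1.645) = 5.29%, so the reference alone should account for about 0.29 points at most, and only in trials that use the robust branch.

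**Step 3: simulation of the whole hybrid under the null.** The SAP program was rebuilt with 400,000 trials for no extremes and 200,000 for each other scenario (Monte Carlo SE about 0.035 to 0.05 points). The code names no weight function, so both Huber and bisquare were run. Only the robust branch's reference was changed, to t with n-3 degrees of freedom. The mixed model kept its containment degrees of freedom, about 214.

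| Extreme slopes | Huber, normal | Huber, t(n-3) | Bisquare, normal | Bisquare, t(n-3) |
|---|---|---|---|---|
| None | 5.31% | 5.27% | 5.41% | 5.36% |
| 1–2% | 5.43–5.56% | 5.27–5.36% | 5.42–5.50% (1–5%) | 5.19–5.33% (1–5%) |
| 5% | 5.70–5.74% | 5.42–5.48% | in row above | in row above |

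The gap is 0.04 to 0.05 points with no extremes and 0.13 to 0.29 points with them. This fits Step 2. The robust branch is used in 47 to 94% of trials with extremes, and 0.29 × 0.47 = 0.14 while 0.29 × 0.94 = 0.27.

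**Step 4: where the rest of the excess comes from.** With no extremes the mixed model alone is at 5.0%, and the robust branch is used in 11 to 12% of trials. Within those trials the error is 7.7% with the normal and still 7.3% with t. Taking 11.5% as the share:
- Effect of the reference: 0.115 × (7.7 - 7.3) = 0.05 points.
- Error implied in the other branch, with the t version: (5.27 - 0.115 × 7.3)/0.885 = 5.0%.

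So in this scenario nearly all the excess over 5% arises in the trials that the outlier rule sends to the robust branch, and most of it remains under t. With 5% extremes and Huber weights, the robust test applied to every trial gives 5.4 to 5.5% even with t, so the small-sample standard error of the M-estimator also contributes.

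**Step 5: power.** With t in the robust branch, hybrid power falls by about 0.1 point with no extremes. With Huber weights it goes from 79.6% to 79.2% (1% extremes, slope 0.4), from 77.5% to 76.9% (2%, slope 0.4) and from 73.0% to 72.2% (5%, slope 0.4).

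**The case against.** The quoted line is simulation code and does not by itself specify the analysis. Section 3.2.2.3.1, which the SAP cites for the robust ANCOVA, is not in the text available for this review, so it may name a reference distribution. This stands: nothing here shows that the SAP leaves the point open. The line is still the only visible statement of how the robust p-value is formed. If the real analysis uses t, the simulations should use it too.

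Three stronger readings are tempting and are not supported.

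- A reader might infer that a t reference would bring the hybrid back to 5.0%. Changing the robust branch alone leaves it at about 5.2 to 5.5%. Values nearer 5.0% with no extremes need the mixed model moved from about 214 to 55 degrees of freedom as well. Its critical value then rises from 1.652 to 1.673, and a branch already at 5.0% falls to P(t214 > 1.673) = 4.8%. That is a separate change.
- A reader might infer that the claim of protection against inflation is wrong. The contents of Table 21 are redacted, so the sponsor's figure cannot be compared. In the rebuild with extreme slopes the mixed model alone is at 5.6 to 6.7% and the hybrid as coded at 5.4 to 5.7%, so the comparison the SAP draws is broadly borne out.
- A reader might infer a material conflict between p-values and the Section 5.6.2 interval. In the robust branch both rest on the normal. In the mixed-model branch the quantiles are 1.652 and 1.645. The interval is also on the scale of exponentiated slopes, so a matching quantile would not guarantee agreement with the test on log slopes.

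**Conclusion.** The point holds as a minor one. The normal reference in the visible robust-branch code is liberal in every scenario examined, by about 0.05 points without extreme slopes and about 0.15 to 0.3 points with them. It accounts for only part of the hybrid's excess over 5%; branch selection on the same data and the M-estimator's small-sample standard error account for the rest.

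The figures rest on settings the code leaves open: weight function, MAD scale, the form of the robust covariance, and containment degrees of freedom for the mixed model. Runs of 100,000 trials without dropout gave 5.3 to 5.6% (normal) and 5.2 to 5.3% (t). Runs with another weighting of the standardized residuals gave 5.4 to 5.8% and 5.3 to 5.5%. Neither alters the conclusion.

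**What to change.** - State in the SAP that the robust ANCOVA p-value and its interval use t with n-3 degrees of freedom, where n is the number of participants contributing a slope, and change the Step 4 line to match.
- State the degrees-of-freedom method for the primary mixed model. Kenward-Roger is already named for the MMRM and would be a natural choice.
- Replace the normal quantile in Section 5.6.2 with the corresponding t quantile for the branch used.
- Rerun Tables 20 and 21 with these references, so that the type I error statement in Section 3.2.2.2 rests on the test that will be used. Report the remaining excess, since this change does not remove it.

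The cost is one line of code, a sentence or two in the SAP and a rerun. Hybrid power falls by about 0.1 point with no extreme slopes and by up to about 1 point with them.

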5.6.1.2 Criteria for 9-HPT, 25FWT and FARS-neuro

Potential outliers will be identified from the weighted standardized residuals, estimated from a robust ANCOVA on individual slopes, with treatment effect (venglustat versus placebo) as factor and the continuous fixed covariate of baseline value.

The robust ANCOVA will be used as primary analysis for the slope analysis

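### The coded outlier trigger scales slope residuals by W rather than its square root, so an extreme progressor with short follow-up can fail to switch the 9-HPT analysis to the robust ANCOVA

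*SAP*

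**What the plan says.** SAP Section 3.2.2.2 makes the mixed model the main 9-HPT analysis and replaces it by a robust ANCOVA on individual slopes when outliers could distort it. It reports that this switching approach (the hybrid) keeps power near 80% in every simulated scenario and guards against Type I inflation.

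Section 5.6.1.2 governs the switch for 9-HPT, 25FWT and FARS-neuro: "Potential outliers will be identified from the weighted standardized residuals". The readable text there gives no formula and no cut-off.

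The simulation code in Section 5.6.3.3 is explicit. Step 2 defines W as each participant's centred sum of squares of assessment times, divided by its mean. Step 4 flags "outlier4 = (abs(W*stdres) > 4", with a matching flag at 3. Step 5 switches when at least one participant exceeds 4 or at least two exceed 3. The Step 4 comment calls the quantity weighted; the Step 5 comment omits the weight. Protocol Section 9.4.1 (Table 6) confirms that the ANCOVA is weighted by the centred sum of squares of time.

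**The concern.** A slope fitted to few, closely spaced visits is noisy. Its error variance is inversely proportional to the centred sum of squares of time, so W acts as an inverse-variance weight. A residual is brought to a common scale by multiplying by the square root of such a weight. Multiplying by W itself shrinks short-follow-up participants too much and slightly inflates completers.

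The trigger decides which analysis carries a co-primary test. If an extreme slope goes unflagged because follow-up was short, the mixed model is kept in the situation the switch was designed for. An unflagged extreme progressor on venglustat costs power; one on placebo makes venglustat look better than it is.

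**Working it through.** **Inputs (SAP).** Section 3.1: "Statistical significance for comparison between venglustat and placebo will be assessed at the Type I error rate of 0.05 one sided". Section 4: "approximately 57 participants will be randomly assigned with a 2:1 randomization ratio to venglustat (n=38) or placebo (n=19" and "This sample size will provide approximately 80% power to detect a difference between venglustat and placebo". Code in Section 5.6.3.3: "let diff = -0.0374,0", "let mS_P = 0.0273", "let sdS = 0.0192"; residual SD 0.0791; visits at 0, 0.25, 0.5, 1, 1.5 and 2 years; 10% dropout over 2 years, drawn independently of slope; extreme slopes 0.4, 0.7 or 0.9. On the log scale 0.7 per year is exp(0.7) = 2.0, a doubling of test time each year.

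**Reproducing the SAP's power.** A Python re-implementation of the code (4,000 trials, no extreme participants) gives 80.9% for the mixed model and 80.9 to 81.2% for the hybrid. This agrees with the stated figure of about 80%.

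**Which scaling is right.** Centred sum of squares (css) = sum of t² − n × mean².
- Completer: 7.5625 − 6 × 0.875² = 2.969.
- Last visit Week 52: 1.3125 − 4 × 0.4375² = 0.547.

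Slope SD = sqrt(0.0192² + 0.0791²/css).
- Completer: sqrt(0.000369 + 0.002108) = 0.0498.
- Last visit Week 52: sqrt(0.000369 + 0.011441) = 0.1087.

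Relative to a completer, the correct shrinkage is 0.0498/0.1087 = 0.46. The square-root rule gives sqrt(0.547/2.969) = 0.43; the coded rule gives 0.547/2.969 = 0.18.

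**Effect on the flag, last visit Week 52.** In the simulated trials W is about 0.20 and sqrt(W) about 0.45. The code shifts an extreme slope by the treatment difference too, so the distance from the arm mean is (extreme slope − 0.0273). Dividing by 0.0498 gives 7.5, 13.5 and 17.5 at slopes 0.4, 0.7 and 0.9; the simulated mean residuals are 7.6, 13.7 and 17.7. Dividing by 0.1087 gives 3.4, 6.2 and 8.0 true SDs.

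One extreme participant on venglustat, 1,500 trials per case. Ranges cover Huber and bisquare weights, because the text says Huber and the code names no weight function:

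| Slope | Score × W | Score × sqrt(W) | Switch, W | Switch, sqrt(W) | Hybrid power, W | Hybrid power, sqrt(W) | Loss, points |
|---|---|---|---|---|---|---|---|
| 0.4 | 1.5 | 3.4 | 10–11% | 36–37% | 75% | 76% | 0.6–1.4 |
| 0.7 | 2.8 | 6.1 | 18–20% | 96% | 69–70% | 76–79% | 7–9 |
| 0.9 | 3.6 | 8.0 | 37–38% | 99.9% | 65–66% | 76–79% | 11–13 |

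The sqrt(W) scores track the true SDs. The W scores all fall below 4. With no extreme participant the coded rule already switches in about 12–13% of trials, so at slope 0.4 it adds no detection.

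**Other configurations.**
- Two on venglustat, last visit Week 52: loss 18.5 to 25 points at slopes 0.7 to 0.9, and 2 to 3.5 at slope 0.4.
- One on placebo, slope 0.7 or 0.9: W gives 7 to 9 points more power.
- One in each arm, slope 0.7: W gives 1 to 1.5 points more.
- One on venglustat, slope 0.4, last visit Week 78 (W = 0.53; scores 7.6 × 0.53 = 4.0 against 7.6 × 0.73 = 5.5): loss 5 to 7 points. The vulnerable exit time therefore moves later for milder slopes.

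**Type I error** (no treatment effect, one on placebo, last visit Week 52; a single run of 1,000 trials per case): 11% with W against 5.4–7.1% with sqrt(W) at slope 0.7; 12% against 5.2–6.9% at slope 0.9. These rates are conditional on the arm.

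**Why the SAP's simulations do not show this.** Under the coded dropout, a given participant has a last visit at Week 52 with probability 0.9^0.5 − 0.9^0.75 = 0.949 − 0.924 = 2.5%. In the five SAP extreme scenarios run (5% at 0.4, 0.7 and 0.9; 2% and 1% at 0.7; 1,200 trials each), W and sqrt(W) differ by at most 0.3 point of power.

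**The case against.** The strongest reply is the planned withdrawal visit. Under footnote a of the protocol's Schedule of Activities (Section 1.3), a participant who stops treatment before Week 104 and leaves the study has the Week 104 assessments, including the 9-HPT. Section 7.2 repeats this, where possible. Participants who stop treatment but stay are followed to Week 104, and all collected data enter the analysis. A withdrawal test at 1.25 years raises css to 2.875 − 5 × 0.6² = 1.075 and W to about 0.20 × 1.075/0.547 = 0.39; a residual of 13.7 then scores 5.3 and is flagged. With 5% extreme participants at slope 0.7 and a withdrawal visit between Weeks 52 and 78, the loss falls to about 1 point.

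This stands for Week 52 leavers who attend, but it moves the gap earlier. A participant last seen at Week 26 with a withdrawal visit at, say, 0.75 years has css 0.875 − 4 × 0.375² = 0.3125 and W of about 0.20 × 0.3125/0.547 = 0.11; 13.7 scores 1.5 with W and 13.7 × 0.34 = 4.7 with sqrt(W). A small run (220 trials, Huber, slope 0.7, Monte Carlo error about 3 points) of a Week 26 leaver with a withdrawal visit gives switch rates of 10% against 69% and power of 72% against 78%.

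Three further replies are fair. The documents give no evidence that fast progressors leave early; the code assumes independence and the analysis assumes missing at random. The quoted line is simulation code, and the operative wording in Section 5.6.1.2 is not fully visible. The robust ANCOVA is reported in any case, although only one analysis carries the co-primary test.

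One reply does not help. If the software's standardized residual already contains sqrt(W), the coded product scales by W^1.5, about 0.20 × 0.45 = 0.09, which shrinks short follow-up further. Nor is the extra power with a placebo outlier a benefit, since it comes with the false-positive increase shown above.

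**Conclusion.** The scaling in the only visible definition of the trigger is wrong, and the SAP's simulations hardly test the case in which it matters. Under the SAP's own dropout there is no measurable harm.

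The harm is conditional. One participant on venglustat with slope 0.7 to 0.9, last seen near Week 52 or leaving between Weeks 26 and 52 with a withdrawal visit, costs roughly 6 to 13 points of hybrid power. One on placebo raises the conditional false-positive rate to about 11 to 12% against 5 to 7%. At slope 0.4 a Week 52 exit has little effect. The results assume dropout linked to an extreme slope and a residual equal to the raw residual divided by the robust scale. The Type I figures rest on one run. The square root is itself approximate (0.43 against 0.46), because slope variance includes a between-participant part.

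A reader might infer that the SAP's 80% power is overstated, or take the two-participant losses of 18.5 to 25 points as an expected or maximum loss. The documents support neither. The 80% reproduces, no document gives such a loss, and its size and sign depend on arm, number, slope and exit time. The correction should be made before unblinding, with medium confidence in its practical importance.

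**What to change.** In SAP Section 5.6.1.2 and in the code, define the flag as abs(sqrt(W) × (slope − fitted)/scale) > 3 or > 4. State that no further multiplication applies if the software's standardized residual already contains sqrt(W). Align the Step 5 comment. The same definition then serves 25FWT and FARS-neuro.

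Re-run the simulations with at least one scenario in which extreme progressors leave early, with and without a withdrawal visit, and report power and Type I error by the arm in which they fall.

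The cost is one term in the code, one sentence in the SAP and a simulation re-run before unblinding. With no extreme participants nothing is lost: in a run of 1,000 trials hybrid power is 82.3% with W and 82.4% with sqrt(W) (Huber), and needless switches fall from 11.9% to 9.8%.
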